Household level process indicators

Treated households will be asked about the nature of their interaction with the Health Ambassadors in the Endline survey:

- What is the name of the Health Ambassador you interacted with?
- Was the Health Ambassador someone that you already knew? Yes/No
- How frequently have you engaged in conversations with the Health Ambassador in the past two months? [Instructions for enumerator: This pertains to the duration from the beginning of the intervention until the date of the end-of-intervention survey.] (Indicate number of interactions)
- I will read you some statements and I would like you to tell me how much you agree or disagree with each statement. Please say whether you strongly agree, agree, neither agree nor disagree, disagree or strongly disagree.
 - D. I learn something new in every discussion I have with the Health Ambassador
 - E. The conversation with the Health Ambassador were interesting.
 - F. I always share the lessons I learn from the discussion with my friends and other family members who do not attend.
- On a scale of 0-10, where 0 is POOR and 10 is EXCELLENT, please rate each of the topics that you discussed with the Health Ambassadors about the vaccine. If you did not cover a topic, let me know and we can skip the topic.
 - A. Benefit of vaccine
 - B. Availability of the vaccine
 - C. Confidence in the vaccine
 - D. Religious/Cultural reasons for not taken the vaccine.
 - E. Others
- Did the Health Ambassador treat you with respect or were they disrespectful?
Respect/Disrespectful
- Would you like it if the Health Ambassador came to speak to you more? Yes/No
- What did you talk about with the Health Ambassador? [open response]

Covariates

We measure the following covariate information in the household roster:

- Whether female for each adult,
- Age of each adult,
- Level of education for each adult,
- Ethnicity of a selected adult,
- Religion of a selected adult,

- Occupational status of a selected adult,
- Household size.
- Measures of opportunity cost from HoH survey:
 - Distance from focal health facility from GPS coordinates
 - How much time would it take to walk to the nearest health facility? (time in minutes)
- Measures of opportunity cost from roster:
 - How many days per week does this person work?
 - How many hours does this person work on a typical work day?

Health Ambassador Surveys

Health Ambassadors Check-In Surveys

At the end of each interaction with a household, the Health Ambassador will complete a brief questionnaire on (i) topics addressed during the discussions with the household, (ii) duration of each discussion topic, (iii) concerns regarding vaccines raised, (iv) the sentiment of the household members after the discussion, and (v) whether the discussion was participatory or tense. This will be submitted securely daily through an online platform.

Health Ambassadors Endline Survey

We will ask the Health Ambassadors to reflect on their experience in a debrief interview, during which they will be asked the following questions:

- What are the key things you learned about the reasons that some people do not get vaccinated?
- What are the key things you learned about how to talk to people so that they will listen to you?
- Did you enjoy this experience – why or why not?
- What would you change about how we asked you to do your job?
- What would you keep the same?

Health Facility Surveys

This survey is addressed to the administrators or any staff members at the health/post center who can represent the administrator's perspective for the targeted health centers in this study. This questionnaire is designed for all the health centers/clinics within the study's scope.

This questionnaire will provide a comprehensive overview of vaccination rates and shed light on the ongoing sensitization activities concerning vaccine hesitancy. Additionally, it will help us explore various contextual aspects related to the topic:

- How many inhabitants does this health center serve?

- Over the past three months, approximately how many patients have sought medical attention at this health/post center?
- In the last 3 months, are the following vaccines available in this health center/health post?
 - [List of vaccines with indication for Yes/No]
- In the last 3 months, are the following vaccines free in this health center/health post?
 - [List of vaccines with indication for Yes/No]
- Over the past three months, for the population that this health/post center is serving, have you been informed of any awareness campaigns, apart from those conducted by the government, health district, and our organization, aimed at reducing vaccine hesitancy for each of the following vaccines:
 - [List of vaccines with indication for Yes/No]
- For each of the vaccines that have been the subject of information campaigns within the localities served by this health center in the past 3 months, what were the awareness-raising strategies employed by the respective organizations?
 - [List of vaccines with indication for type of information campaign]
- Which organization(s) led this vaccination campaign?
 - [List of vaccines with space to indicate organization(s)]
- For each of the vaccines provided at this health center, what is the vaccination rate by June 2023?
 - [List of vaccines with space to indicate rate]
- In this health/post center, have you faced any instances of vaccine shortages in the last 3 months for each of the following vaccines?
 - [List of vaccines with indication for Yes/No]

Note: For each country (Côte d'Ivoire, Malawi, Senegal, and Zimbabwe), the list of vaccines will be limited to those specifically targeted by the study. This list of vaccines varies from one country to another.

Analysis Plan

Estimating Average Effects with Household Data

For the vaccine trust and other attitudinal measures in the individual survey, we will use a hierarchical index strategy.¹ All outcome measures will first be standardized in terms of control group standard deviations. That is, we will construct a standardized sum of scores index for each of the 4 groupings listed above. Then, we will construct a global index that is a standardized sum of the grouping indices. Indexes will be oriented so that more positive values indicate a movement in the beneficial direction. For a given index, we will estimate average treatment effects using the following regression specification:

$$y_i = \alpha + \beta Treated_i + Rand. Block FE_{b[i]} + X_i' \gamma + \epsilon_i , \quad (1)$$

where i indexes the individual-survey respondent for household i , and $Rand. Block FE_{b[i]}$ and the covariate vector X_i are defined the same way as in equation (1). We calculate cluster-robust

¹ The approach follows that of Casey et al. (2012).

standard errors taking the error term ϵ_{vji} to be clustered at the level of the randomization cluster. Again, we hypothesize that $\beta > 0$, and we test using a two-sided test (allowing for the possibility that effects could go in the opposite direction as what is hypothesized) with 95% confidence. We will use a hierarchical statistical significance testing strategy:

- For the global index, we will use the standard asymptotic p value and a two-sided null hypothesis with 95% confidence.
- If the global p-value rejects the null, then for the grouping-specific indices, we will use a Benjamini-Hochberg FDR correction for the 4 p-values.
- For any grouping index that rejects the null, we will use the Benjamini-Hochberg FDR correction for the item level p-values.

For estimating peer effects, we will use the same specification (2), with l indexing the peer respondent and $Treated_i$ indicating the treatment status of the person that recommended them.

For our behavioral outcome measured in the household roster, we will estimate the average treatment effect on the pooled vaccination rate using the following regression specification:

$$y_{vji} = \alpha + \beta Treated_i + Vaccine FE_v + Rand. Block FE_{b[i]} + X_{ji}'\gamma + \epsilon_{vji} , \quad (2)$$

where v indexes the vaccine, j indexes the individual adult in the household roster, i indexes the household, and $b[i]$ indexes the randomization block for household i . The variable $Treated_i$ is an indicator for whether the household is in a treated cluster or not. Then, $Vaccine FE_v$ are fixed effects (dummy variables) for the different vaccines and $Rand. Block FE_{b[i]}$ are fixed effects (dummy variables) for the randomization blocks. The covariate vector X_{ji} includes the following elements:

- Indicator for female of individual j ,
- Age for individual j ,
- Level of education for individual j ,
- Pre-intervention vaccination rate in the household's cluster.

We calculate cluster-robust standard errors taking the error term ϵ_{vji} to be clustered at the level of the randomization cluster. We hypothesize that $\beta > 0$, and we test using a two-sided test (allowing for the possibility that effects could go in the opposite direction as what is hypothesized) with 95% confidence. If we reject the null, we will then test effect on each individual vaccine, using the Benjamini-Hochberg FDR correction for the vaccine-level p-values.

Effect Heterogeneity with Household Data

We propose an exploratory analysis of background conditions that may moderate the size of the treatment effects on behavior and attitudes. These include:

Respondent attributes:

- Gender,
- Age,
- Level of education,
- Ethnic group (coded for collectivist norms),
- Proximity to health center.

Health ambassador attributes:

- Gender,
- Age,
- Type of degree program,
- Co-ethnicity with respondent,
- Personality measure of empathy (empathy assessment scale).

This analysis will take advantage of the random assignment of health ambassadors to households. We will perform a “dummy” random assignment for the control group so that we know, for each control group household, which of the health ambassadors *would* have treated them, counterfactually.

These analyses will be conducted as separate one-way interaction regressions with the following specifications:

$$y_{vji} = \alpha + \beta_1 Treated_i + \beta_2 W_{ji} + \beta_3 Treated_i * W_{ji} + Vaccine FE_v + Rand. Block FE_{b[i]} + X_{ji}'\gamma + \epsilon_{vji} , \quad (4)$$

$$y_i = \alpha + \beta_1 Treated_i + \beta_2 W_i + \beta_3 Treated_i * W_i + Rand. Block FE_{b[i]} + X_i'\gamma + \epsilon_i , \quad (5)$$

where W_{ji} or W_i refers to the background characteristic in question. We will use FDR control on the p-values for the respondent attribute (as one family of estimates) and then the health ambassador attributes (as a separate family) interaction effect estimates.

Mechanisms through which the intervention may increase vaccine uptake

To identify the mechanisms through which the intervention may increase the primary outcome of interest, we estimate the following two equations:

$$M_{ji} = \alpha^M + \beta^M Treated_i + Rand. Block FE_{b[i]} + X_{ji}'\gamma^M + \epsilon_{vji}^M \quad (6)$$

$$Y_{ji} = \alpha^Y + \beta^Y Treated_i + \kappa M_{vji} + Rand. Block FE_{b[i]} + X_{ji}'\gamma^Y + \epsilon_{vji}^Y \quad (7)$$

The “first stage” effect of the Health Ambassador treatment on the mediating variables is captured by β^M and then the extent to which a mediating variable is responsible for transmitting the effect of the HA treatment onto vaccine outcomes is given by $\beta^M \kappa$. We will use the Imai et al. “mediation” software in R to implement this analysis. We hypothesize that the intervention will improve vaccine trust through subjects' acceptance of the benefits of vaccination, subjects' access to vaccination and affordability. Additionally, the subjects are aware of the availability of vaccines and the benefits and risks associated with the vaccine and are motivated to seek vaccination. Moreover, the subjects accept the medical system as a trustworthy healthcare provider.

Descriptive Analyses of Process and Context

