Please give your level of agreement with each statement using the scales provided (where 1 = strongly disagree/strongly against vaccination and 10 = strongly agree/strongly in favor of vaccination).

- 1.1. Thinking about vaccination in general, would you say you are...
1=strongly against vaccination, 10=strongly in favour of vaccination
- 1.2. I generally trust vaccine manufacturers or pharmaceutical companies
1=strongly disagree, 10=strongly agree
- 1.3. I generally trust the {country specific health department}
1=strongly disagree, 10=strongly agree
- 1.4. I understand how vaccination helps my body fight infectious disease
1=strongly disagree, 10=strongly agree
- 1.5. I feel it is important that I get vaccinated
1=strongly disagree, 10=strongly agree
- 1.6. Vaccination forms part of a healthy lifestyle
1=strongly disagree, 10=strongly agree

The items are summed to create a composite vaccine trust score. We will standardize in terms of control group standard deviations.

Secondary outcome measures

These secondary outcomes will be measured through a household questionnaire at baseline (before the intervention) and endline (after the intervention). The following questions will be asked to adult members of the household.

1. Vaccine uptake

- 1.1 For each vaccine and each target household members, the individual questionnaire will indicate whether the respondent (i) did not verbally affirm receiving the vaccination or provide documentation, (ii) verbally affirmed vaccination but did not provide documentation, or (iii) provided documentation of vaccination.

For respondents who have not been vaccinated due to time constraints or limited access to health centers, the survey will capture their intention to receive the vaccine if they were at a health center using the following question: Are you planning to be vaccinated for the [country specific disease] vaccine?

2. Knowledge about the disease: I will read you some statements and I would like you to tell me how much you agree or disagree with each statement. Please say whether you strongly agree, agree, neither agree nor disagree, disagree, or strongly disagree.
 - 2.1. [The targeted disease name] exists.
 - 2.2. I am aware of how [The targeted disease name] is transmitted.
3. To the best of my knowledge, [Targeted disease name from the list] require vaccines for their cure?
4. Vaccine/disease knowledge:

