- 7.2. Which of the following statements best describes your status regarding the [XXX] vaccine? (I am fully vaccinated; I am not vaccinated, but if someone brought it to me I would take it; I am not vaccinated, and I do not want to be vaccinated)
 - 7.2.1. [XXX] = ask for all target vaccinations in the country
- 7.3. Suppose that COVID cases started to rise again. If the health ministry recommended that you get vaccinated or boosted for COVID, would you get it? (Definitely not, Probably not, maybe/maybe not, probably yes, definitely yes).
- 7.4.
8. Trust in healthcare system:
 - 8.1. In the past 3 months how often have you visited a nurse, doctor, or community health worker for any health? (Yes/No)
 - 8.2. In the past 3 months how often have you visited a nurse, doctor, or community health worker for vaccination related issues? (Yes/No)
 - 8.3. In the past 3 months how often have you visited a nurse, doctor, or community health worker for vaccination related issues? (Never, only sometimes. often, always)
 - 8.4. In general, how often have you visited a nurse, doctor, or community health worker for any health-related issues? (Never, only sometimes. often, always)
 - 8.5. In general, how often have you visited a traditional medicine practitioner or a traditional healer for any health-related issues? (Never, only sometimes. often, always)
 - 8.6. Which of the following statements is closest to your view? Choose Statement 1 or Statement 2.

Statement 1: Whenever I experience a health problem, I tend to seek medical advice from professionals in modern medicine.

Statement 2: Whenever I face a health issue, my preference is to consult traditional medicine practitioners for guidance and treatment.

Agree with neither [Do not read]
 - 8.7. How confident are you in the government's healthcare system to help prevent you and your loved ones from getting very sick from diseases? (Not at all; a very little bit; somewhat; mostly confidence; totally confident)
 - 8.8. If you wanted to verify the safety of a medication or vaccination, what is the best source to do so? (Do not read responses: Health Ambassador, doctor, nurse, health

worker, religious leader, chief or traditional leader, other relative or household member, internet/social media, books, other: specify).

- 8.9. I would like to offer you an opportunity to sign up to receive Ministry of Health bulletins via text [ASSUMING SUCH A SERVICE EXISTS]. Would you like me to sign you up for this service? (Yes/No)

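### The endline planning question goes only to people unvaccinated for reasons of time or access, a filter the intervention can shift, so intention among those asked is not a randomised comparison

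*Protocol*

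**What the plan says.** In the protocol, Secondary outcome measures, item 1.1 (Vaccine uptake) records each vaccine at three levels of evidence: neither affirmed nor documented, "verbally affirmed vaccination but did not provide documentation, or (iii) provided documentation of vaccination". It then adds a planning question with a restriction: "For respondents who have not been vaccinated due to time constraints or limited access to health centers, the survey will capture their intention". The question itself is "Are you planning to be vaccinated for the [country specific disease] vaccine".

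The timing is given at the head of the same section: "These secondary outcomes will be measured through a household questionnaire at baseline (before the intervention) and endline (after the intervention".

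Item 7.2 (Vaccine confidence) asks for vaccination status or willingness without reference to the reason. Two of its three answers are "I am not vaccinated, but if someone brought it to me I would take it; I am not vaccinated, and I do not want to" (the second is cut short here), and its scope is "ask for all target vaccinations in the country". Item 7.3, also unrestricted, asks whether the person would follow a ministry recommendation if COVID cases rose again.

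The analysis plan has one behavioural outcome, for which "we will estimate the average treatment effect on the pooled vaccination rate" by equation (2). The equation carries vaccine fixed effects. It does not say which evidence level sets the outcome to 1.

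**The concern.** Whether a person is asked about plans depends on the reason given for not being vaccinated. At baseline that does no harm to the comparison. At endline the reason is itself an outcome. A persuaded refuser who has not yet gone may now cite time or distance and enter the group. A willing person who has gone leaves it. The section on mechanisms lists access and affordability, and awareness of availability, among the routes by which the intervention is expected to work, so on the protocol's own reasoning the filter may move with treatment.

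Two things are at stake. A difference in intention between treated and control respondents who were asked could reflect who was asked rather than what they intend. And the adults the trial most wants to move, those unvaccinated because of hesitancy, give no answer to this item; no later analysis can recover answers that were not collected.

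There is a smaller, separate point. Treated households are to have at least two private conversations promoting vaccination, and control households none. An unverified verbal claim is where over-reporting could differ by arm, and the protocol does not state whether such claims count as vaccinated.

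**Working it through.** The protocol gives no figure for the planning question, so there is none to reproduce. The calculations below show what the rule can do. Apart from the 7-point target and the rate implied by it, all inputs are assumptions.

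**1. Filtered intention, varying the movers.** Let A be the share of unvaccinated adults who cite time or access, a the share of these who plan to be vaccinated, m the share of the other unvaccinated adults whom treatment moves into the time-or-access group, c the intention of those movers after treatment, and h the intention of the other adults without treatment. Nobody is vaccinated in this version.

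- Control, among those asked: a.
- Treated, among those asked: [A·a + (1−A)·m·c] / [A + (1−A)·m].
- True gain over all unvaccinated adults: (1−A)·m·(c−h).

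With A = 0.30, a = 0.70, m = 0.10 and h = 0.05, the treated value is (0.21 + 0.07c)/0.37 and the true gain is 0.07(c − 0.05).

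| Movers' intention c | Control, asked | Treated, asked | Filtered contrast (points) | True gain (points) |
|---|---|---|---|---|
| 0.30 | 70.0% | 62.4% | −7.6 | +1.75 |
| 0.50 | 70.0% | 66.2% | −3.8 | +3.15 |
| 0.70 | 70.0% | 70.0% | 0.0 | +4.55 |
| 0.90 | 70.0% | 73.8% | +3.8 | +5.95 |

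The true gain is positive in every row. The filtered contrast is negative in two rows, zero in one and positive in one.

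**2. The same with some people vaccinated.** Take 100 unvaccinated adults per arm. In control, 30 cite time or access and 20 of them plan to go: 20/30 = 67%. In the treated arm, 10 of those 20 are vaccinated and leave, so 20 remain, 10 of them planning. Another 14 former refusers enter, 7 of them planning. The group is now 34 with 17 planning: 17/34 = 50%. Vaccinated or planning, over all 100, is 20 in control and 10 + 17 = 27 in the treated arm. The filtered figure falls by 17 points and the full-denominator figure rises by 7. These inputs were chosen to show a reversal; they do not predict one.

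**3. Verbal-only claims.** Under Cluster selection, 0.15 SD is equated with 7 percentage points. The implied SD is 7/0.15 = 46.7 points, so p(1−p) = 0.218 and p is about 0.32 or 0.68. Suppose verbal-only claims are counted, the true effect is zero, and false affirmation among unvaccinated adults is higher in the treated arm by d. The spurious effect is (1−p)·d.

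| True rate p | d = 2 points | d = 5 points | d = 10 points |
|---|---|---|---|
| 10% | 1.8 | 4.5 | 9.0 |
| 32% | 1.4 | 3.4 | 6.8 |
| 50% | 1.0 | 2.5 | 5.0 |

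At p = 0.32, a gap of 0.07/0.68 = 10.3 points would imitate the whole 7-point target. With d = 0 there is no spurious effect.

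**The case against.** The protocol does not put the planning item into equation (2) or plan an arm comparison within the filtered group. That stands: the fault lies in the data collected under a named secondary outcome, not in a specified test. The full questionnaire is a separate document, so the exact skip pattern cannot be confirmed from the protocol.

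Items 7.2 and 7.3 put willingness to everyone, and 7.2 comes close to a vaccinated-or-willing measure over all respondents. This also stands, and it rules out the inference that hesitant adults are never asked about willingness. The items are not full substitutes: 7.2 supposes the vaccine is brought to the person, and 7.3 covers COVID only, in a hypothetical resurgence. Neither asks about a plan to be vaccinated.

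A reader might infer from equation (2) that verbal and documented vaccination are merged. The text does not support that. The three levels are recorded separately, and pooling is across vaccines, as the vaccine index and fixed effects show. How the levels are coded is simply unstated, and a separate analysis plan may settle it. Nor can one conclude that treatment biases both behavioural measures: only one is named, and bias in it needs verbal-only claims to count and misreporting to differ by arm.

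The 32% rate is solved back from a power statement that used district-level COVID rates. It is not the multi-vaccine rate in households chosen for having a never-vaccinated adult. Also, the visits are to the head and another adult, while Table A1 gives 12,618/3,773 = 3.3 adults per household, so not every adult counted need have been visited. Both points weaken the third calculation as a guide to size.

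**Conclusion.** The point holds for the planning question. Its filter is applied at endline to a reason that treatment can change, so a comparison of intention among those asked is not protected by randomisation, and its sign can differ from that of the true change. This rests on the wording of item 1.1, the endline timing and the protocol's own list of mechanisms. It does not rest on the illustrative figures. Size and direction are unknown: under one set of assumptions the filtered contrast runs from −7.6 to +3.8 points. The primary outcome, the vaccine trust score, is not touched, and items 7.2 and 7.3 limit the loss.

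On evidence levels the conclusion is narrower: the coding of the outcome in equation (2) is left open where over-reporting could differ by arm. Whether it does is not known.

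**What to change.** **Planning question.** At endline, put it to every adult not vaccinated for each target vaccine, in both arms and whatever the reason. Analyse vaccinated-or-planning with all adults in the denominator. If endline is already complete, report the filtered item descriptively and use item 7.2 for the arm comparison. The cost is one more question for more respondents, and those newly asked will have no matching baseline answer, since baseline is finished.

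**Evidence level.** State how verbal-only and documented vaccination enter equation (2). Run it with documented vaccination only and again with verbal-only claims added, and report the verbal-only share by arm. The levels are already collected, so this costs one further regression and a table. Documented vaccination should not be the sole condition for claiming an effect, because it counts vaccinated people without a card as unvaccinated.

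**Instrument.** Item 1.1 places uptake in the individual questionnaire, and the text before equation (2) places it in the household roster. Reconcile the two, so that it is clear who answers for each adult.
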